5.4. Analysis Variables

Variables to be summarized include demographics and baseline characteristics, medical (non-ocular) and ocular history, concomitant medications, and study drug accountability.

Efficacy variables include:

- DCNVA (i.e., Near VA)
- BCDVA (i.e., Distance VA)

[figure not shown]
- DCIVA (i.e., Intermediate VA)
- Pupil diameter (PD)

Safety variables include:

- Conjunctival hyperemia (eye redness) measured with a CCLRU card 4-point scale:
 - None (0) = Normal Appears white with a small number of conjunctival blood vessel easily observed.
 - Mild (+1) = Prominent, pinkish-red color of both the bulbar and palpebral conjunctiva.
 - Moderate (+2) = Bright, scarlet red color of the bulbar and palpebral conjunctiva.
 - Severe (+3) = Beefy red with petechiae, dark red bulbar and palpebral conjunctiva with evidence of subconjunctival hemorrhage.
- Subjective ocular tolerability measured on a 4-point scale:
 - 0 – No discomfort
 - 1 – Mild discomfort
 - 2 – Moderate discomfort
 - 3 – Severe discomfort
- AEs
- Vital signs (HR and BP)
- IOP
- Biomicroscopy
- Ophthalmoscopy
- Urine pregnancy tests for females of childbearing potential

6. SAMPLE SIZE

A sample size of approximately 140 subjects (40 for Nyxol + LDP and Placebo alone arms and 30 for each of the other 2 arms) who are evaluable for efficacy is needed for the study. The primary treatment comparison will be Nyxol + LDP compared to Placebo alone.

Subjects will be randomized 4:3:3:4 to Nyxol + LDP, Nyxol + No Treatment 2 (Nyxol alone), Placebo + LDP, and Placebo + No Treatment 2 (Placebo alone), respectively.

It is assumed that there will be approximately 7% drop-out between Visit 1 and end of Visit 2. To account for this drop-out, a total of approximately 152 subjects will be randomized into the study.

7. GENERAL CONSIDERATIONS

7.1. Analysis Populations

The following analysis populations will be defined for this study.

7.1.1. Modified Intention-to-Treat (mITT)

The mITT population will include all randomized subjects who received at least one drop of Treatment 1 and were administered Treatment 2 (LDP or No Treatment). The mITT population will be used to analyze selected efficacy endpoints, with subjects included in their randomized treatment regardless of the treatment they actually received.

7.1.2. Per Protocol Population (PP)

The PP population included all subjects in the mITT population who received one drop of Treatment 1 the day prior to Visit 2 and were administered Treatment 2 at Visit 2, had binocular DCNVA and BCDVA in photopic conditions at Baseline (Visit 1) and at Visit 2 time 1 hour, and had no major protocol deviations. The PP population will be used for the primary endpoint analysis and to analyze all efficacy endpoints, with subjects included in their randomized treatment regardless of the treatment they actually received.

7.1.3. All Randomized Population (ARP)

The ARP will include all randomized subjects. This population is also known as the Intention-to-Treat (ITT) population. The ARP will be used in confirmatory efficacy analyses, with subjects included in their randomized treatment regardless of the treatment they actually received.

7.1.4. Safety Population (SP)

The SP will include all randomized subjects who have received at least one drop of study treatment (Treatment 1 or Treatment 2). The SP will be used to summarize safety variables, using the actual treatment a subject received.

7.2. Covariates and Subgroups

7.2.1. Planned Covariates

Planned covariates include baseline values for the given assessment.

7.2.2. Planned Subgroups

Subgroup analyses by irides type (light, dark) will be completed for efficacy endpoints.

Other possible subgroups include age, sex, and race.

7.3. Management of Analysis Data

7.3.1. Data Handling

Data from unscheduled visits will not be included in the analysis of efficacy or safety but will be listed.

7.3.2. Missing Data

The primary efficacy endpoint is the percentage of subjects with ≥ 15 letters of improvement from baseline in photopic binocular DCNVA on Visit 2 at 1 hour with Nyxol + LDP compared to Placebo alone. For the analysis of the primary efficacy endpoint, imputation will be performed for missing efficacy data as specified in Section 7.3.2.3 for the analysis using the mITT, as well as the PP, if required. Confirmatory analyses may be performed using the ARP, also using imputation for missing data.

Otherwise, there will be no substitutions made to accommodate missing data points for efficacy data. All data recorded on the CRF will be included in data listings that will accompany the CSR.

Safety data will be imputed in limited situations. If the severity of an AE is missing, then the severity will remain missing. If relationship of the AE to study drug is missing, the relationship will remain missing. Missing or partial dates for AEs or concomitant medications will be imputed as described in Section 7.3.2.1. Otherwise, all summaries of safety endpoints will be completed using observed cases in the SP; no imputation will be completed.

7.3.2.1. Handling of Missing Date Values

Partial or Missing Dates

The following conventions will be used to impute missing portions of dates for AEs and concomitant medications, if warranted. Note that the imputed values outlined here may not always provide the most conservative date. In those circumstances, the imputed value may be replaced by a date that will lead to a more conservative analysis.

A. Start Dates

- 1) If the year is unknown, then the date will not be imputed and will be assigned a missing value.
- 2) If the month is unknown, then:
 - i) If the year matches the first dose date year, then impute the month and day of the first dose date.
 - ii) Otherwise, assign 'January.'
- 3) If the day is unknown, then:

- i) If the month and year match the first dose date month and year, then impute the day of the first dose date.
- ii) Otherwise, assign the first day of the month.

B. Stop Dates

- 1) If the year is unknown, then the date will not be imputed and will be assigned a missing value.
- 2) If the month is unknown, then assign 'December.'
- 3) If the day is unknown, then assign the last day of the month.

7.3.2.2. Missing Baseline Data

Every effort will be made to ensure that accurate baseline information on the subjects is collected. In the event that a subject is missing baseline information, the subject will be included in the SP for assessment of safety and excluded from the primary analyses. Each case of missing baseline data will be evaluated for potential inclusion in the exploratory endpoints. All baseline data will be observed cases, without imputation.

7.3.2.3. Imputation Methods

Imputation for efficacy data will only be performed for the primary efficacy endpoint using the mITT and ARP, as well as the PP, if required. If 5% or fewer data are missing at the Visit 2, 1 hour time point in the Nyxol + LDP and Placebo alone treatment groups, an analysis with last observation carried forward (LOCF) for missing data will be applied within a treatment group. Neither the baseline (Visit 1) nor the Visit 2, 0 minutes time points will be used for imputation. If more than 5% of data are missing at the Visit 2, 1 hour time point in the Nyxol + LDP and Placebo alone treatment groups, multiple imputation will be employed to analyze incomplete data sets under the assumption that the mechanism responsible for the missing data is at worst characterized as missing at random (MAR).

Multiple imputation is a simulation-based approach where missing values are replaced by multiple Bayesian draws from the conditional distribution of missing data given the observed data and covariates, creating multiple completed data sets. These completed datasets can then be analyzed using standard analysis methods. Rubin (1987) presented rules for how to combine the multiple sets of estimates to produce overall estimates, confidence intervals (CIs), and tests that adequately incorporate missing data uncertainty.

Missing values for DCNVA will be imputed simultaneously based on an underlying joint normal distribution using a Markov Chain Monte Carlo (MCMC) method.

The imputations will be done separately for each treatment group and will include the following variables in the imputation model: binocular photopic DCNVA at Visit 2 (30 minutes, 1 hour, 2 hours, 3 hours, 4 hours, 6 hours). No imputation will be applied to the Visit 2, 0 minutes time point.

The number of imputations will be set to 500. The outcomes of interest (change from baseline) will be calculated from these imputed datasets. The treatment difference for each

imputed dataset will be evaluated using logistic regression. See Section 9.1 for details on these models. The estimates and standard errors (SEs) of the odds ratios based on the 500 imputed datasets are then combined by [REDACTED]

[REDACTED] The odds ratios with the corresponding 95% CI will also be presented.

Example [REDACTED]

[REDACTED]

[REDACTED]

[REDACTED]

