4.2. Study Endpoints

4.2.1. Primary Endpoints

Endpoints will be evaluated following administration of masked Nyxol or Placebo (Treatment 1) at or near bedtime for 3 to 4 days, with administration of LDP or No Treatment (Treatment 2) at the next visit (Visit 2) in the morning. Analysis will be completed for 4 treatment arms:

- Nyxol + LDP
- Nyxol + No Treatment 2 (Nyxol alone)
- Placebo + LDP (LDP alone)
- Placebo + No Treatment 2 (Placebo alone)

The primary efficacy endpoint is the percent of subjects with ≥ 15 letters of improvement in photopic binocular DCNVA on Visit 2 at 1 hour with Nyxol + LDP compared to Placebo alone. The improvement in binocular DCNVA for each subject is relative to the subject's own Baseline value (Visit 1). The analysis of the primary endpoint will be completed for the per-protocol (PP) population, as defined in Section 7.1.2 below.

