5. STUDY METHODS

5.1. General Study Design and Plan

This is a placebo-controlled, double-masked, randomized, 4-arm Phase 2 study in males and females between 40 to 64 years of age with presbyopia. A sample size of approximately 152 subjects will be randomized into 1 of 4 treatment arms with the expectation that approximately 140 subjects will be evaluable for efficacy, where evaluable is defined as having received at least one drop of Treatment 1, administered Treatment 2 (LDP or No Treatment), and completed at least one photopic binocular DCNVA measurement after Treatment 2.

Subjects are evaluated for safety and efficacy following administration of masked Nyxol or Placebo (Treatment 1) at or near bedtime for 3 to 4 days, with administration of LDP or No Treatment (Treatment 2) at the next visit (Visit 2) in the morning. Measurements are made at multiple visits and timepoints, and analysis compares 4 treatment arms:

- Nyxol + LDP
- Nyxol + No Treatment 2 (Nyxol alone)
- Placebo + LDP
- Placebo + No Treatment 2 (Placebo alone)

Subjects are randomized 4:3:3:4 into the above groups.

After randomization, masked Treatment 1 study medications (Nyxol or Placebo) is dispensed. Treatment 1 study medication is taken by the subject at or near bedtime (approximately 8PM-10PM) starting the night of Visit 1 (Screening/Baseline) or at the appropriate evening in order for Treatment 1 to be taken daily for 3 to 4 consecutive days immediately prior to Visit 2.

Treatment 2 (LDP or No Treatment) is unmasked and is administered at Visit 2 by a designated, unmasked, Site Staff member, distinct from the Site Staff member recording measurements/assessments.

Treatment 1 (Nyxol or Placebo) is administered to both eyes (OU) by the subject.

Treatment 2 (LDP or No Treatment) is administered OU by the Site Staff.

The study eye is defined as the eye with worse Baseline photopic DCNVA. In the case where both eyes have the same Baseline photopic DCNVA, the study eye will be the right eye (OD). The non-study eye will be the fellow eye. The study eye and fellow eye will both be evaluated at all assessments.

The schedule for assessments and timing of events is presented in Table 1.

Table 1 Visit Schedule

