9.1.1. Primary Efficacy Analysis

The primary efficacy endpoint is the percent of subjects with ≥ 15 letters of improvement in photopic binocular DCNVA on Visit 2 at 1 hour with Nyxol + LDP compared to Placebo alone in the study eye. If the analysis using the PP Population shows a positive effect for Nyxol at the 0.05 level of significance, the primary endpoint will be considered met. The primary efficacy endpoint will be analyzed using a logistic regression model with treatment and light/dark irides as factors and the baseline DCNVA as a covariate. The percentage of subjects in each treatment group meeting the criteria, the odds ratio (OR) with 95% CI, and p-value will be provided. Example SAS code is as follows:

[REDACTED]

By including irides type as a factor in the primary efficacy analysis model, the model efficiency as well as a change in the treatment effect will be increased. Including this factor in the model will also make the results more generalizable to other studies in which the sample characteristics may differ from the current study [2].

In addition, the primary efficacy endpoint will be analyzed by light/dark irides using the same model indicated above but without irides as a factor. For this subgroup analyses, observed case data only will be used; that is, missing values will not be imputed.

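### The multiple-imputation model omits baseline DCNVA, so a subject with no reading after Treatment 2 gets a 1-hour score unrelated to his or her own baseline

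*SAP*

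**What the plan says.** SAP 7.3.2.3 uses last observation carried forward if 5% or fewer of the 1-hour values are missing in the two primary arms, and multiple imputation otherwise. The multiple imputation is joint normal, by MCMC, run separately in each treatment group. It will "include the following variables in the imputation model: binocular photopic DCNVA at Visit 2 (30 minutes, 1 hour", followed by the readings at 2, 3, 4 and 6 hours. Neither baseline nor irides type is listed. The section then states: "The outcomes of interest (change from baseline) will be calculated from these imputed datasets". Just after the carry-forward rule it also says: "Neither the baseline (Visit 1) nor the Visit 2, 0 minutes time points will be used for imputation".

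Other sections bear on this:

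- SAP 4.2.1 measures improvement against the subject's "own Baseline value (Visit 1). The analysis of the primary endpoint will be completed for the per-protocol (PP) population".
- SAP 9.1.1 fits a "logistic regression model with treatment and light/dark irides as factors and the baseline DCNVA as a covariate".
- SAP 7.3.2.2 states: "All baseline data will be observed cases, without imputation". A subject without baseline is left out of the primary analyses.
- SAP 7.1.1 admits to the mITT anyone who "received at least one drop of Treatment 1 and were administered Treatment 2 (LDP or No Treatment"). No later reading is required. By contrast, SAP 5.1 counts a subject as evaluable only if he or she also "completed at least one photopic binocular DCNVA measurement after Treatment 2".
- SAP 7.1.2 requires observed baseline and 1-hour readings for the per-protocol (PP) set, which decides the primary endpoint.
- SAP 9 makes the ARP analysis optional.

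**The concern.** The outcome is built from two numbers, the 1-hour score and the baseline. The imputation model ignores the second, although it is observed for every subject analysed and is a covariate in the analysis model.

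Where some Visit 2 readings exist, they carry most of the baseline information. Where none exist, the listed model has no subject-specific predictor. The draw is then unrelated to the subject's baseline, and subtracting that baseline makes poor-baseline subjects responders too often and good-baseline subjects too seldom. The missing-at-random assumption is also weakened: if loss depends on baseline, it holds only given baseline, and the model does not condition on it.

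What is at stake is the supporting evidence. The ARP is the plan's intention-to-treat set and the only efficacy set that keeps subjects who leave before Visit 2.

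**Working it through.** **1. The plan's own figure.** SAP 6: 140 evaluable with 7% drop-out gives 140 / 0.93 = 150.5, consistent with about 152 randomized. At 4:3:3:4 the two primary arms hold 152 × 8/14 = 86.9 subjects, or about 43 each. The power and response rates behind the 38 per arm in Protocol 9.1 are redacted, so effect sizes below are assumed.

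**2. Error for one subject.** Write the 1-hour score as Y = a + bB + e, with B the baseline, b the slope and e a residual of SD s. For a subject whose baseline is d letters below the arm mean, the correct expected change is the arm's mean gain + (1 − b)d. The listed model gives the mean gain + d. The overstatement is b × d. For example, with d = 6 it is 4.2 letters at b = 0.7 and 6.0 letters at b = 1.0, against a 15-letter threshold.

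**3. Spread of change.** With sB the baseline SD:

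- true SD = √[((b − 1)sB)² + s²]
- imputed SD = √[(b·sB)² + s² + sB²]

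Assumed: baseline normal with mean 46 and SD 6-8 before truncation at 50 or 54 letters (Protocol inclusion criterion 6 requires 20/50 or worse, which SAP Table 2 puts at 50-54 letters); b = 0.7 or 1.0; s = 5-7.

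| Cap, SD | sB | b | s | True SD | Imputed SD | Ratio |
|---|---|---|---|---|---|---|
| 50, 6 | 4.38 | 0.7 | 5 | 5.17 | 7.32 | 1.42 |
| 50, 6 | 4.38 | 0.7 | 7 | 7.12 | 8.81 | 1.24 |
| 54, 8 | 6.35 | 1.0 | 5 | 5.00 | 10.28 | 2.06 |
| 54, 8 | 6.35 | 1.0 | 7 | 7.00 | 11.38 | 1.63 |

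Over the whole grid the true SD is 5.0-7.3, the imputed SD 7.3-11.4 and the ratio 1.24-2.06.

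**4. Effect on the odds ratio.** Simulation with 43 per arm, 3 per arm with no reading after Treatment 2, mean gain 6-8 (placebo) and 13-16 (combination), 500 replicates × 12 imputations, and a Firth-penalized logistic model with treatment and baseline (irides omitted). There were 48 settings per loss mechanism; the Monte Carlo SE of the shifts was 0.007-0.015.

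| | Random loss | Poor-baseline loss |
|---|---|---|
| Placebo responders among the missing: true | 8-18% | 7-33% |
| – SAP list | 15-27% | 51-80% |
| – with baseline added | 9-18% | 12-36% |
| Log-OR shift, SAP list | -0.01 to -0.14 (median -0.05) | -0.03 to -0.32 (median -0.12) |
| Log-OR shift, with baseline | -0.02 to +0.02 | -0.03 to +0.03 |

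The SE of the log-OR under random loss is 0.53-0.69. A median shift of -0.05 multiplies the odds ratio by e^-0.05 = 0.95; -0.12 multiplies it by 0.89. All 96 settings moved toward the null. With sparse placebo response (about 4%, SE 0.85-0.93) the shift was -0.07 to -0.26 under random loss and -0.33 to -0.59 under poor-baseline loss.

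A separate simulation (baseline SD 7, 1-hour SD 8, mean changes 3 and 13, 7% wholly missing) gave these median log-ORs for full data, SAP list and SAP list plus baseline:

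- correlation 0.3: 2.34, 2.34, 2.34
- correlation 0.5: 2.70, 2.65, 2.69
- correlation 0.7: 3.41, 3.18, 3.36

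**5. Chance that multiple imputation is used.** Pooled over 86 subjects, 5% is 4.3, so 5 missing are needed. The documents do not say how many of the 7% drop-outs miss the 1-hour reading.

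| Share of drop-outs missing 1 hour | Missing rate | P(at least 5 of 86) | P(at least 3 of 43 in both arms) |
|---|---|---|---|
| All | 7% | 0.73 | 0.34 |
| Three quarters | 5.25% | 0.47 | 0.16 |
| Half | 3.5% | 0.18 | 0.04 |
| A quarter | 1.75% | 0.02 | 0.002 |

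At the smallest pooled trigger (2 + 3 missing) the shift was -0.01 to -0.12 under random loss and -0.03 to -0.36 under poor-baseline loss.

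**The case against.** **The plan may already cover it.** SAP 7.3.2.3 describes multiple imputation in general as conditioning on observed data and covariates, SAP 7.2.1 names baseline values as the planned covariates, and the example code is redacted. This stands as a limit on certainty. But the general description is textbook background, SAP 7.2.1 does not mention imputation, and the one explicit variable list omits baseline. The sentence barring baseline, if it applies beyond carry-forward, forbids it.

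**The reach is narrow.** This stands. The PP decision is untouched, the ARP analysis is optional, and the 5% trigger must be passed. Subjects with some readings are barely affected: at baseline SD 7, 1-hour SD 8, correlation 0.5 with baseline and 0.8 within the visit, the variance ratio is 113/57 = 1.98 with no other reading, 1.20 with one and 1.05 with five. In the mITT, one wholly missing subject per arm shifts the log-OR by -0.01 to -0.04 (random loss) or -0.04 to -0.13 (poor-baseline loss). Even that needs other subjects to miss the 1-hour reading, because 2 of about 80 would not trigger multiple imputation.

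**The shift is small and usually conservative.** This also stands. A clear upward shift (+0.10 to +0.18) appeared only when the combination arm alone lost 3 poor-baseline subjects, and 3 of 86 (3.5%) is below the pooled trigger. The poor-baseline mechanism is a scenario; the documents neither support it nor rule it out.

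**Irides type.** The main simulation left it out, so the case for adding it rests on consistency with the SAP 9.1.1 model.

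**Conclusion.** The point holds as an improvement at no cost; it does not threaten the primary result. As printed, the imputation model is narrower than the analysis model and omits one of the two components of the outcome. For subjects with no reading after Treatment 2, the imputed change is too variable whenever baseline and 1-hour acuity are positively correlated. That correlation is an assumption, though a natural one for repeat acuity readings in the same subject. The likely effect on a supporting odds ratio is a modest pull toward the null: under random loss a median of -0.05 on the log scale, less than a tenth of its SE, and more than double that if poor-baseline subjects are the ones lost. All sizes rest on assumed letter-score distributions. Confidence is moderate because the code is redacted.

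**What to change.** In SAP 7.3.2.3:

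- Add baseline (Visit 1) binocular photopic DCNVA to the by-arm imputation model, alongside the six Visit 2 readings.
- Add irides type as a binary covariate, not as a further by-group split, to match the analysis model.
- State that the sentence excluding baseline and the 0-minute value means that baseline may not be carried forward, and that it does not bar baseline as a predictor in multiple imputation.

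The carry-forward branch, the 5% rule and the 0-minute rule can stay as they are. The cost is two variables already collected, one imputation step to amend and one clarifying sentence. No data, visits or subjects are added.

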7.4. Planned Study Analyses

7.4.1. Statistical Summaries: Descriptive and Inferential

Categories for data presentation and analysis will consist of each treatment group: Nyxol + LDP, Nyxol + No Treatment 2 (Nyxol alone), Placebo + LDP, Placebo + No Treatment 2 (Placebo alone).

All statistical tests will be two-sided and a difference resulting in a p-value of less than or equal to 0.05 will be considered statistically significant. The p-values for the analysis of secondary efficacy endpoints and safety endpoints will be considered descriptive. All p-values will be rounded to and displayed in four decimals. If a p-value less than 0.0001 occurs, it will be shown in tables as <0.0001.

Descriptive summaries of variables will be provided where appropriate. For continuous variables, the number of non-missing values (n), mean, standard deviation, median, minimum, and maximum will be tabulated by treatment group. For categorical variables, the counts and proportions of each value will be tabulated by treatment group. Expansion of descriptive table categories within each treatment may occur if such elaborations are thought to be useful.

All study-related data collected will be presented in listings. Study-related data not subject to analysis according to this plan will not appear in any tables or graphs but will be included in the data listings.

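### SAP 7.3.2.3 names the odds ratios and their SEs as the quantities pooled across imputations; it should name the log odds ratio, and the code should be checked

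*SAP*

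**What the plan says.** SAP section 7.3.2.3 (Imputation Methods) limits efficacy imputation to the primary endpoint. It applies to the mITT population and the ARP, and to the PP population if required. LOCF is used when 5% or fewer of the 1-hour values are missing in the two primary arms. The other branch, which begins "If more than 5% of data are missing at the Visit 2, 1 hour time point", leads to multiple imputation.

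The multiple-imputation steps visible in that section are:

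- "The number of imputations will be set to 500".
- Each dataset is analysed by logistic regression. Section 9.1.1 specifies a "logistic regression model with treatment and light/dark irides as factors and the baseline DCNVA as a covariate".
- "The estimates and standard errors (SEs) of the odds ratios based on the 500 imputed datasets are then combined by" is followed by a redaction.
- The next visible sentence is "The odds ratios with the corresponding 95% CI will also be presented". An example follows, also redacted.

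Earlier in the section the framework is named: "Rubin (1987) presented rules for how to combine the multiple sets of estimates". No visible text in either document mentions a log odds ratio, a regression coefficient, or a transformation before pooling.

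**The concern.** Rubin's rules average the estimates, add within- and between-imputation variance, and form a symmetric interval. They need an estimator that is roughly normal. In logistic regression that is the coefficient, the log odds ratio. The odds ratio itself is strongly right-skewed with about 40 subjects per arm, so a symmetric interval around it reaches far too low and its lower limit can be negative.

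PP membership requires the 1-hour measurement. The mITT and ARP analyses are therefore the ones that show whether leaving out subjects without it affects the result. If the visible sentence were programmed as written, these analyses could appear to contradict a positive PP result for a purely technical reason.

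**Working it through.** **Inputs.** Arm sizes come from SAP section 6: "40 for Nyxol + LDP and Placebo alone arms and 30 for each of the other 2 arms". The protocol's sample-size section also uses 38 per primary arm. The test level is in SAP section 7.4.1: "All statistical tests will be two-sided and a difference resulting in a p-value of less than or equal to 0.05 will be considered statistically significant". Expected response rates are redacted, so the rates below are assumptions.

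**The plan's own figure.** The documents show no figure on the pooling scale. The one visible sample-size result can be reproduced: 140 / (1 − 0.07) = 150.5, or 151, against approximately 152 stated. This confirms the arm sizes but does not bear on the scale.

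**Formulas.** For a 2×2 table with cells a, b, c, d:

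- SE(log OR) = √(1/a + 1/b + 1/c + 1/d)
- Log-scale CI = exp(log OR ± 1.96 × SE)
- SE(OR) = OR × SE(log OR), by the delta method
- OR-scale CI = OR ± 1.96 × SE(OR)

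**Example, 24/40 against 8/40.**

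- OR = (24/16) / (8/32) = 6.0.
- SE(log OR) = √(1/24 + 1/16 + 1/8 + 1/32) = √0.2604 = 0.510.
- Log scale: exp(1.792 ± 1.000) = 2.2 to 16.3; z = 1.792/0.510 = 3.51, p about 0.0004.
- OR scale: SE = 6.0 × 0.510 = 3.06; 6.0 ± 6.0 = about 0.0 to 12.0. A Wald test of OR = 1 gives z = 5.0/3.06 = 1.63, p = 0.10.

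**Other assumed rates, 40 per arm.**

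| Responders | OR | Log-scale 95% CI | Log-scale p | OR-scale 95% CI |
|---|---|---|---|---|
| 20/40 v 6/40 | 5.7 | 1.95 to 16.5 | 0.0014 | −0.4 to 11.7 |
| 20/40 v 4/40 | 9.0 | 2.70 to 30.0 | 0.00035 | −1.84 to 19.84 |
| 30/40 v 8/40 | 12.0 | 4.18 to 34.45 | 0.000004 | −0.66 to 24.66 |

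**Does it depend on the assumed rates?** The OR-scale lower limit is OR × (1 − 1.96 × SE). To exceed 1 it needs SE below 1/1.96 = 0.510 and OR above 1/(1 − 1.96 × SE). At 40 per arm the smallest possible SE is √(4/20) = 0.447, with every cell at 20. Even there the OR would have to exceed 1/(1 − 0.8765) = 8.1, yet that table has OR = 1.

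All tables without zero cells that favour the combination were then enumerated. Among those with log-scale p < 0.05, the OR-scale interval includes 1 in 485 of 485 at 40 per arm and 426 of 426 at 38 per arm. Among those with p < 0.001 the counts are 288 of 288 and 249 of 249.

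**What pooling adds.** Rubin's total variance is W + (1 + 1/500) × B, where W is the within- and B the between-imputation variance. The tables above have no B term, which can only widen the interval.

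**When the rule would run.** The two primary arms hold about 152 × 8/14 = 87 randomized subjects. Reading the threshold as pooled over both arms, 5% of 87 is 4.3, so five missing values trigger multiple imputation. The assumed 7% drop-out is about 6. An ARP analysis could therefore cross the threshold if most drop-out falls before the 1-hour reading. The mITT is less likely to, because its members must have reached Treatment 2 in clinic.

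**The case against.** A reader might infer that the plan pools odds ratios rather than log odds ratios. The documents do not establish this. The sentence is cut off by redaction exactly where the combining rule would stand, the example is redacted too, and redacted text is not missing from the plan. A transformation may be stated there. The word *also* in "The odds ratios with the corresponding 95% CI will also be presented" fits a procedure that pools the coefficient first and then reports odds ratios. Because each dataset is fitted by logistic regression, the phrase about odds ratios may be loose shorthand for the model's treatment estimates. All of this stands, and it limits the point to the visible wording.

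A reader might also infer that the primary conclusion is at risk. It should not be. SAP section 9.1.1 decides success on the PP population, and section 7.1.2 admits only subjects with the 1-hour binocular measurement, so that analysis should have nothing to impute. The ARP analysis is optional. An error of this kind would lose a supportive finding, not create a false positive, and a negative limit for an odds ratio would be visible in the output.

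The tables are unadjusted, whereas the planned model includes irides and baseline DCNVA, and no visible text specifies a Wald test of OR = 1. Exact figures would differ. The objection does not remove the visible statement itself: it names the quantities to be combined, and they are on a scale unsuited to the rules the section cites.

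**Conclusion.** The point holds as a correction to wording, with a code check. If SAP 7.3.2.3 is followed literally, pooled odds-ratio intervals at about 40 per arm would include 1 even where the log-scale analysis is clearly significant. Whether the hidden rule or code does this cannot be determined from the documents.

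The consequence is confined to the mITT and optional ARP analyses of the primary endpoint, and only above 5% missing at 1 hour. It is conservative in direction. The size rests on assumed response rates, unadjusted tables and delta-method SEs; the enumeration shows that the direction does not depend on which rates are assumed.

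**What to change.** Reword the sentence in SAP 7.3.2.3 along these lines: *The treatment log odds ratio (logistic regression coefficient) and its SE from each imputed dataset are combined by Rubin's rules. The pooled estimate and its 95% confidence limits are exponentiated for presentation as an odds ratio, and the p-value is taken from the pooled log odds ratio.*

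Before unmasking, confirm that the example and production code pool the coefficient and its SE. If the redacted text already says so, only the visible sentence needs to be brought into line. The cost is one sentence and one code check, with no effect on data collection or on the PP analysis.
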